9.4.9 Interim Analyses

No formal interim analysis is planned for the study.

9.5 Determination of Sample Size

This is a complete block three-way crossover study. Assuming a residual CV of 6% for peak FEV₁, 70 patients will give an 80% power to detect a pairwise difference in peak FEV₁ of 5.1%. Assuming a mean baseline FEV₁ of 1.3 liters this will correspond to a difference of about 50 mL.

Verona Pharma plc CONFIDENTIAL Page 52 of 66

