Duration of Treatment:	The approximate planned duration of participation for each patient will be up to 61 days: 7 to 14-day screening period, up to 9 days treatment (three treatment periods of 3 days each separated by 7 to 14 days) and an end of study visit 4 to 10 days after the last treatment visit (Day 4 of Treatment Period 3).
Statistical Methods:	Treatments will be compared using analysis of covariance adjusting for treatment, period, patient and baseline. Multiplicative models will be used for FEV ₁ and outcome from whole body plethysmography and additive models for blood pressure, pulse rate and ECG heart rate. RPL554 doses will first be compared to placebo using a closed test procedure starting with the highest dose of RPL554.
Sample Size:	This is a complete block three-way crossover study. Assuming a residual coefficient of variation of 6% for peak FEV ₁ , 70 patients will give an 80% power to detect a pairwise difference in FEV ₁ of 50 mL.

Verona Pharma plc CONFIDENTIAL Page 8 of 66

TABLE OF CONTENTS AND LIST OF TABLES AND FIGURES

Table of Contents

SPC	NSOI	R SIGNA	ATURE PAGE	2
INV	ESTI	GATOR	SIGNATURE PAGE	3
COl	NFIDE	ENTIAL	ITY STATEMENT	3
COl	NTAC	T LIST .		4
DET	TAIL (OF AME	ENDMENTS SINCE THE PREVIOUS VERSION	5
SYN	IOPSI	S		6
TAE	BLE O	F CONT	TENTS AND LIST OF TABLES AND FIGURES	9
	Tabl	e of Cor	ntents	9
	List	of Table	es and Figures	12
LIS	ΓOF	ABBRE	VIATIONS AND DEFINITION OF TERMS	13
1	INT	RODUC	TION	14
	1.1	Diseas	e and Study Medication Review	14
	1.2	Summ	ary of Risks and Benefits	16
2	OBJ	ECTIVE	ES	17
	2.1	Primar	y Objective	17
	2.2	Second	dary Objectives	17
	2.3	Explor	ratory Objectives	17
3	INV	ESTIGA	ATIONAL PLAN	18
	3.1	Overal	1 Study Design and Plan Description	18
	3.2	Discus	sion of Study Design, including the Choice of Control Groups	19
	3.3	Planne	d Duration of the Study	19
	3.4	Definit	tion of the End of the Study	19
4	SEL	ECTION	N OF STUDY POPULATION	20
	4.1	Inclusi	on Criteria	20
	4.2	Exclus	ion Criteria	21
	4.3	Remov	val of Patients from Therapy or Assessment	22
		4.3.1	Study Treatment Discontinuation	22
		4.3.2	Patient Withdrawal	22
		4.3.3	Study Discontinuation	23
		4.3.4	Replacement Policy	23
5	STU	DY TRI	EATMENTS	24
	5.1	Study '	Treatments Administered	24
	5.2	Identit	y of Study Treatments	24
		5.2.1	RPL554 and Placebo	24
		5.2.2	Tiotropium/olodaterol Respimat®	24
	5.3	Prepara	ation and Labelling	25
		5.3.1	Nebulized RPL554 and Placebo	25
		5.3.2	Tiotropium/olodaterol	25

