4.3.4 Replacement Policy

It is planned to have 70 evaluable patients (i.e., completing at least two treatment periods). Withdrawn patients may need to be replaced to meet this target.

Verona Pharma plc CONFIDENTIAL Page 23 of 66

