9.4.5 Efficacy/Pharmacodynamics

FEV₁ and FVC will be summarized as actual and change from baseline using descriptive statistics over time.

The peak effect on FEV_1 during these time intervals will be computed as the maximum value in the 4 hours after dosing. The average effect will be calculated as the AUC divided by the length of the time interval of interest. For analysis, the peak, average and trough FEV_1 will be divided by the pre-dose Day 1 baseline value.

Computed pharmacodynamic parameters for FEV_1 will be compared between the three study treatments using analysis of covariance (ANCOVA) models with fixed factors for treatment, period and patient, and using the pre-dose Day 1 baseline value as a covariate. FEV_1 will be analyzed using multiplicative models, which means that data (dependent and baseline) are logged prior to analysis and the result then transformed back to the linear scale giving treatment differences as ratios of geometric means.

Primarily the combination RPL554+tiotropium/olodaterol will be compared to tiotropium/olodaterol alone for each of the two doses of RPL554. Results of the comparisons will be expressed as the mean geometric ratio with 95% confidence intervals and associated, 2-sided, p-value.

Onset of action will be summarized by treatment and a Kaplan-Meier plot illustrating time to onset constructed.

Outcomes from the whole body plethysmography at 1.25 hours post-dose on Day 1 and 1.25, 8.25 and 12.25 hours post-dose on Day 3 will be compared in the same way as FEV₁ using multiplicative ANOVA models. The baseline of the visit (pre-first dose in a treatment period) will be used as covariate in these models.

The use of rescue medication during the study visits will be summarized by treatment, and, if appropriate, a Kaplan-Meier plot illustrating time to first use of rescue constructed.

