	2.1.8. RPL554 steady state pharmacokinetics (AUC _{0-12h} , Cmax, time to maximum co	
7)	31	

Document: Z:\ RPL554\UYA25849\Biostatistics\Documentation\SAP\Verona RPL554-CO-204 SAP v1.0

Author: [name] Version Number: 1.0

Version Date: [18OCT2018]

Template No.: CS_TP_BS016 Revision 5 Reference: CS_WI_BS005

Effective Date: 01Apr2018

17. REFERENCES	41
APPENDIX 1. PROGRAMMING CONVENTIONS FOR OUTPUTS	42
IQVIA Output Conventions	42
Table and Listing Output Conventions	42
Figure Output Conventions	44
Dates & Times	44
Spelling Format	45
Presentation of Treatment Groups	45
Presentation of Treatment Sequences	45
Presentation of Visits	46
Listings	46
APPENDIX 2. PARTIAL DATE CONVENTIONS	46
Algorithm for Treatment Emergence of Adverse Events	47
Algorithm for Prior / Concomitant Medications	48

Document: Z:\ RPL554\UYA25849\Biostatistics\Documentation\SAP\Verona RPL554-CO-204 SAP v1.0

Author: [name] Version Number: 1.0

Version Date: [18OCT2018]

Template No.: CS_TP_BS016 Revision 5 Reference: CS_WI_BS005

Effective Date: 01Apr2018

Page 9 of 50

1. Introduction

This document describes the rules and conventions to be used in the presentation and analysis of efficacy and safety data for protocol RPL554-CO-204. It describes the data to be summarized and analyzed, including specifics of the statistical analyses to be performed. The statistical analysis plan (SAP) is based on the final protocol version 2.0, dated 10JUL2018.

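### The sample-size figures contradict each other: 5.1% of 1.3 L is 66 mL, not about 50 mL, and 70 patients at a 6% CV reach 80% power at about 2.9%

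*Protocol*

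**What the plan says.** Protocol section 9.5 gives the whole justification. The design is stated first ("This is a complete block three-way crossover study"), then the variability ("Assuming a residual CV of 6% for peak" FEV₁), then the claim that "70 patients will give an 80% power to detect a pairwise difference in peak FEV₁ of 5.1" per cent, and finally the conversion: "Assuming a mean baseline FEV₁ of 1.3 liters this will correspond to a difference of about 50 mL".

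The Sample Size entry of the synopsis repeats the 6% CV and says "70 patients will give an 80% power to detect a pairwise difference" of 50 mL. It gives neither the percentage nor the baseline.

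Three other places bear on the calculation:

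- Section 4.3.4 defines who counts towards the 70: "It is planned to have 70 evaluable patients (i.e., completing at least two treatment periods").
- Section 9.4.5 analyses FEV₁ on the log scale, "giving treatment differences as ratios of geometric means".
- Section 9.4 sets two-sided testing at 5%. SAP section 7.4 tests the two doses in fixed sequence, each at the full 5%, so no alpha is split.

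The SAP has no sample-size section.

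**The concern.** Section 9.5 presents 5.1% and about 50 mL as the same difference on a 1.3 L baseline, and a one-line multiplication shows that they are not. A 6% within-patient CV with 70 patients in a complete crossover is also a precise design, and 5.1% looks far too large to be the difference it detects with only 80% power.

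These are the only planning figures in the documents. As they stand, a reader cannot say whether the target was 5.1%, 50 mL (3.85%) or something else, or whether the CV, the percentage, the baseline or the power is the wrong entry. A synopsis reader cannot see the conflict, because the percentage and the baseline are missing there.

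**Working it through.** **Inputs.** From protocol 9.5: residual CV 6%, n = 70, power 80%, difference 5.1%, baseline 1.3 L, about 50 mL, complete three-way crossover. From protocol 9.4 and SAP 7.4: two-sided 5% for each comparison. From protocol 9.4.5: log scale, with patient, period, treatment and baseline in the model.

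**Step 1: percentage against mL.**

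- 0.051 × 1300 mL = 66.3 mL
- 50 / 1300 = 3.85%
- The two agree only at a baseline of 50 / 0.051 = 980 mL

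**Step 2: trying to reproduce 5.1% at 80% power.**

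- Log-scale SD: √ln(1 + 0.06²) = 0.05995
- SE of a pairwise difference, all three periods complete: 0.05995 × √(2/70) = 0.01013
- Residual df: 210 − (70 + 2 + 2 + 1) = 135

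Power from the noncentral t:

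| Difference | Log difference | Log difference / SE | Power |
|---|---|---|---|
| 5.1% | ln(1.051) = 0.04974 | 4.91 | 99.8% |
| 50 mL on 1.3 L (3.85%) | ln(1 + 50/1300) = 0.03774 | 3.72 | 95.9% |
| 2.90% (37.7 mL on 1.3 L) | 0.02859 | 2.82 | 80% |

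The stated figure is not reproduced. A normal approximation gives 2.88% and a paired t-test with 69 df gives 2.92%, so the choice of method does not explain the gap.

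**Step 3: other readings of the calculation** (difference at 80% power unless noted).

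- One-sided 5%: 2.6%
- Bonferroni for two comparisons: 3.2%; for three: 3.4%
- 90% power: 3.4%; 95%: 3.75%; 99%: 4.5%
- The 70 patients split into three parallel arms of about 23, with the 6% CV as the SD: 5.04% (normal) to 5.12% (t, 67 df)

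Only the last comes close to 5.1%. It is a possible origin, but nothing in the documents says so, and it is not this design.

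**Step 4: incomplete patients.** Section 4.3.4 counts a patient after two periods. With fixed patient and period effects, six sequences and Period 3 missing:

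| Patients without Period 3 | Power for 50 mL | 80% power at |
|---|---|---|
| 7 of 70 | 95% | 2.98% (39 mL) |
| 14 of 70 | 94% | 3.08% (40 mL) |
| all 70 (extreme) | 74% | 4.15% (54 mL) |

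Even in the extreme case, power for 5.1% is 93%, not 80%. The last digits shift slightly with how the missing patients fall across sequences.

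**Step 5: base of the mL conversion.** The model estimates a ratio of peak FEV₁ values, but section 9.5 converts with baseline FEV₁. The documents give no expected peak. Assuming a placebo-period peak between 1.3 and 1.7 L:

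| Base | 2.90% equals | Power for 50 mL | 5.1% equals |
|---|---|---|---|
| 1.30 L | 37.7 mL | 96% | 66 mL |
| 1.45 L | 42.1 mL | 91% | 74 mL |
| 1.60 L | 46.4 mL | 85% | 82 mL |
| 1.70 L | 49.3 mL | 81% | 87 mL |

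A higher base brings 50 mL closer to 80% power but moves 5.1% further from 50 mL. No single base reconciles all three figures.

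**Step 6: dependence on the CV** (70 patients completing all periods, 1.3 L base).

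| Residual CV | Power for 50 mL | Power for 5.1% |
|---|---|---|
| 6% | 96% | 99.8% |
| 7% | 89% | 99% |
| 8% | 79% | 96% |
| 9% | 69% | 90% |
| 10% | 60% | 83% |

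Power is 80% for 50 mL at a CV of 7.9%, and for 5.1% at about 10.5%. At 10.5%, power for 50 mL is only about 56%.

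**The case against.** The strongest objection concerns consequence and scope. No test, estimate or interval uses these numbers, and at a 6% CV with complete data the trial has more than 80% power for either stated difference, so this could be called editorial. The all-two-period case is also implausible. It assumes fixed patient effects, whereas the SAP's model code makes the patient effect random, which can recover some information from incomplete patients. The upper end of the assumed peak range has no source in the documents.

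These remarks are fair, but they touch only steps 4 and 5, which test possible rescues. Steps 1 and 2 need neither.

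A second objection is that the reassurance rests on the 6%, for which section 9.5 cites no source. If the true CV is just under 8% or higher and 50 mL is the target, power is no longer understated. This stands, and it is why the CV must be confirmed before replacement figures are written. It does not argue against keeping 70 patients, since power can be restated at whatever CV is confirmed.

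A third concerns versions. The SAP "is based on the final protocol version 2.0, dated 10JUL2018", while the supplied protocol describes itself as the first version. Section 9.5 may since have been corrected. That limits the finding to the supplied text. If a correction exists, the sponsor can close the point by citing it.

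**Conclusion.** The concern holds. In the supplied protocol, 5.1%, about 50 mL on 1.3 L and 80% power cannot all be true, and neither difference follows from the stated CV and sample size. The mL conversion is off by 16 mL (66.3 against about 50). At a 6% CV, 80% power belongs to about 2.9% (38 mL on 1.3 L).

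The conversion error rests on no modelling assumption. The power figures assume 70 patients completing all three periods, a two-sided 5% test, log-scale analysis, and 6% as the within-patient CV. Under those assumptions the error is conservative. The planning statement is wrong as written and should be corrected, but the trial is not shown to be underpowered.

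**What to change.** Keep 70 patients. Confirm the residual CV from the data it came from, recompute, and put one consistent set of CV, percentage difference, mL difference and power in both section 9.5 and the synopsis. Say whether the mL figure is taken on baseline or on peak FEV₁. Do not choose a CV so that the stated power comes out.

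If 6% is confirmed, wording such as this would do:

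> With a residual CV of 6%, 70 patients completing all three periods give 80% power (two-sided 5%) to detect a 2.9% difference in peak FEV₁ (about 38 mL, converted on a baseline of 1.3 L) and about 96% power for 50 mL (3.8%). Power is lower if some patients complete only two periods.

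If another CV is confirmed, use the same sentence with recomputed figures; at 8%, for example, power for 50 mL is about 79%. The cost is a change of wording in two places. Patient numbers and the analysis stay as they are.

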10 ETHICAL CONSIDERATIONS

10.1 Guidelines

The study will be performed in accordance with ICH GCP guidelines, the principles outlined in the Declaration of Helsinki (1996), the protocol and applicable regulatory requirements.

10.2 Ethics and Regulatory Approval

The Sponsor will supply all background data necessary to enable submission to the appropriate ethics committees and regulatory authorities. The study will not commence before formal ethical and regulatory approvals have been granted.

All changes or revisions of this protocol will be documented. The reason for the amendment will be stated. The Sponsor will ensure ethical and regulatory approval is obtained for all substantial amendments to the original approved documents.

10.3 Informed Consent Process

It is the responsibility of the Investigator to obtain written informed consent from patients. All consent documentation must be in accordance with applicable regulations and GCP. Each patient is requested to sign and date the informed consent form after (s)he has received and read the patient information sheet and received an explanation of what the study involves, including but not limited to: the objectives, potential benefits and risk, inconveniences and the patient's rights and responsibilities. Patients will be given adequate time to evaluate the information given to them before signing the informed consent form.

One original of the signed informed consent form must remain on file and must be available for verification by the study monitor at any time. A second original of the informed consent form plus the patient information sheet must be given to the patient or the patient's legally authorized representative.

10.4 Patient Confidentiality

Data collected during this study may be used to support the development, registration or marketing of the study medication. The Sponsor will control all data collected during the study and will abide by the European Union Directive on Data Privacy concerning the processing and use of patient's personal data. For the purpose of data privacy legislation, the Sponsor will be the data controller.

After patients have consented to take part in the study, their medical records and the data collected during the study will be reviewed by the Sponsor and/or its representatives. These records and data may, in addition, be reviewed by the following: independent auditors who validate the data on behalf of the Sponsor; regulatory authorities and the ethics committee which gave its approval for this study to proceed.

Although patients will be known by a unique number, their initials will also be collected and used to assist the Investigator to reconcile data clarification forms, for example, that the results of study assessments are assigned to the correct patient. The results of this study containing the unique number, but not the patient's initials and relevant medical information may be recorded and transferred to and used in other countries throughout the world, which may not afford the same level of protection that applies within the European Union. The purpose of any such transfer would be to support regulatory submissions made by the Sponsor in such countries.

Verona Pharma plc CONFIDENTIAL Page 53 of 66

10.5 Record Maintenance/Retention

The Investigator will retain the originals of all source documents generated at the location where the study is being conducted, either: 1) until after regulatory agency approval is obtained for the study medication in the country/countries in which the results of this study comprise the submission dossier, or 2) for a period of 2 years after the report of the study has been finalized, in the absence of a regulatory approval. After that time, all study-related documents will be archived according to GCP regulations.

Verona Pharma plc CONFIDENTIAL Page 54 of 66

11 FINANCE AND INSURANCE

Financial arrangements are detailed in the Investigator Agreement between the Sponsor and Investigator.

The Sponsor will arrange clinical study insurance to compensate patients for any potential injury or death caused by the study.

Verona Pharma plc CONFIDENTIAL Page 55 of 66

12 PUBLICATION POLICY

The publication policy is detailed in the Investigator Agreement between the Sponsor and Investigator.

Verona Pharma plc CONFIDENTIAL Page 56 of 66

14 APPENDICES

14.1 Birth Control Methods For Women of Childbearing Potential Which May Be Considered As Highly Effective

(Adapted from the Clinical Trial Facilitation Group, Heads of Medicines Agencies, 2014)

I. Definitions

Woman of Childbearing Potential

A woman is considered fertile following menarche and until becoming postmenopausal unless permanently sterile. Permanent sterilization methods include hysterectomy, bilateral salpingectomy, and bilateral oophorectomy.

Women in the following categories are not considered women of childbearing potential:

- 1. Premenopausal female with one of the following:
 - Documented hysterectomy
 - Documented bilateral salpingectomy
 - Documented bilateral oophorectomy

Note: Documentation can come from the study center staff's: review of participant's medical records, medical examination, or medical history interview.

2. Premenarchal

3. Postmenopausal female

Females who are postmenopausal (age-related amenorrhea ≥ 12 consecutive months and increased FSH >40 mIU/mL), or who have undergone hysterectomy or bilateral oophorectomy are exempt from pregnancy testing. If necessary to confirm postmenopausal status, an FSH will be drawn at Screening.

Females on hormone replacement therapy (HRT) and whose menopausal status is in doubt will be required to use one of the non-hormonal highly effective contraception methods if they wish to continue their HRT during the study. Otherwise, they must discontinue HRT to allow confirmation of postmenopausal status before study enrollment.

II. Methods

For the purpose of this guidance, methods that can achieve a failure rate of less than 1% per year when used consistently and correctly are considered as highly effective birth control methods. Such methods include:

- Combined (oestrogen and progestogen containing) hormonal contraception associated with inhibition of ovulation:
 - Oral
 - Intravaginal
 - Transdermal
- Progestogen-only hormonal contraception associated with inhibition of ovulation¹:
 - Oral

Verona Pharma plc CONFIDENTIAL Page 59 of 66

- Injectable
- Implantable¹
- Intrauterine device¹
- Intrauterine hormone-releasing system¹
- Bilateral tubal occlusion¹
- Vasectomized partner^{1,2}
- Sexual abstinence³

¹Contraception methods that in the context of this guidance are considered to have low user dependency

² Vasectomised partner is a highly effective birth control method provided that partner is the sole sexual partner of the trial participant and that the vasectomized partner has received medical assessment of the surgical success ³ In the context of this guidance sexual abstinence is considered a highly effective method only if defined as refraining from heterosexual intercourse during the entire period of risk associated with the study treatments. The reliability of sexual abstinence needs to be evaluated in relation to the duration of the clinical trial and the preferred and usual lifestyle of the patient

Verona Pharma plc CONFIDENTIAL Page 60 of 66

14.2 Tiotropium/Olodaterol Prescribing Highlights and Instructions for Use

Note: The information below is excerpted from the US package insert for tiotropium/olodaterol. Full prescribing information in the US is available at:

 $\underline{http://docs.boehringer-ingelheim.com/Prescribing\%20Information/PIs/Stiolto\%20Respimat/stiolto.pdf}$

Full prescribing information in the UK is available at:

http://www.spioltorespimatpi.uk

HIGHLIGHTS OF PRESCRIBING INFORMATION
These highlights do not include all the information needed to use
STIOLTO RESPIMAT safely and effectively. See full prescribing
information for STIOLTO RESPIMAT.

STIOLTO* RESPIMAT* (tiotropium bromide and olodaterol) inhalation spray, for oral inhalation use Initial U.S. Approval: 2015

WARNING: ASTHMA-RELATED DEATH See full prescribing information for complete boxed warning.

- Long-acting beta₂-adrenergic agonists (LABA) such as olodaterol, one of the active ingredients in STIOLTO RESPIMAT, increase the risk of asthma-related death. (5.1)
- A placebo-controlled study with another long-acting betagadrenergic agonist (salmeterol) showed an increase in asthmarelated deaths in patients receiving salmeterol. (5.1)
- This finding of an increased risk of asthma-related death with salmeterol is considered a class effect of LABA, including olodaterol, one of the active ingredients in STIOLTO RESPIMAT. The safety and efficacy of STIOLTO RESPIMAT in patients with asthma have not been established. STIOLTO RESPIMAT is not indicated for the treatment of asthma. (4, 5.1)

-INDICATIONS AND USAGE-

STIOLTO RESPIMAT is a combination of tiotropium, an anticholinergic and olodaterol, a long-acting beta;-adrenergic agonist (LABA) indicated for: The long-term, once-daily maintenance treatment of airflow obstruction in patients with chronic obstructive pulmonary disease (COPD) (1.1)

Important limitations

- STIGLTO RESPIMAT is NOT indicated to treat acute deterioration of COPD. (1.2)
- STIOLTO RESPIMAT is NOT indicated to treat asthma. (1.2)

-DOSAGE AND ADMINISTRATION-

- For oral inhalation only.
- Two inhalations of STIOLTO RESPIMAT once-daily at the same time of day. (2)

--- DOSAGE FORMS AND STRENGTHS-

Inhalation spray: Each actuation from the mouthpiece contains 3.124 mcg tiotropium bromide monohydrate, equivalent to 2.5 mcg tiotropium, and 2.736 mcg olodaterol hydrochloride, equivalent to 2.5 mcg olodaterol.

Two actuations equal one dose. (3)

-CONTRAINDICATIONS-

- All LABAs are contraindicated in patients with asthma without use of a long-term asthma control medication. (4) STIOLTO RESPIMAT is not indicated for the treatment of asthma. (1.2)
- Hypersensitivity to tiotropium, ipratropium, olodaterol, or any component of this product. (4)

-WARNINGS AND PRECAUTIONS-

- LABA increase the risk of asthma related death. (5.1)
- Do not initiate STIOLTO RESPIMAT in acutely deteriorating COPD patients. (5.2)
- Do not use for relief of acute symptoms. Concomitant short-acting betagagonists can be used as needed for acute relief. (5.2)
- Do not exceed the recommended dose. Excessive use of STIOLTO RESPIMAT, or use in conjunction with other medications containing LABA can result in clinically significant cardiovascular effects and may be fatal. (5.3)
- Immediate hypersensitivity reactions: Discontinue STIOLTO RESPIMAT at once and consider alternatives if immediate hypersensitivity reactions, including angioedema, bronchospasm, or anaphylaxis, occur. (5.4)
- Life-threatening paradoxical bronchospasm can occur. Discontinue STIOLTO RESPIMAT immediately. (5.5)
- Use with caution in patients with cardiovascular or convulsive disorders, thyrotoxicosis, or sensitivity to sympathomimetic drugs. (5.6, 5.7)
- Worsening of narrow-angle glaucoma may occur. Use with caution in patients with narrow-angle glaucoma and instruct patients to consult a physician immediately if this occurs. (5.8)
- Worsening of urinary retention may occur. Use with caution in patients with prostatic hyperplasia or bladder-neck obstruction and instruct patients to consult a physician immediately if this occurs. (5.9)
- Be alert to hypokalemia and hyperglycemia. (5.11)

-ADVERSE REACTIONS-

The most common adverse reactions (>3% incidence and more than an active control) were nasopharyngitis, cough, and back pain.

To report SUSPECTED ADVERSE REACTIONS, contact Boehringer Ingelheim Pharmaceuticals, Inc. at [contact] or [contact] TTY, or FDA at [name] or www.fda.gov/medwatch.

-DRUG INTERACTIONS-

- Other adrenergic drugs may potentiate effect. Use with caution. (5.3, 7.1)
- Xanthine derivatives, steroids, diuretics, or non-potassium sparing diuretics may potentiate hypokalemia or ECG changes. Use with caution. (7.2, 7.3)
- MAO inhibitors, tricyclic antidepressants, and drugs that prolong QTc interval may potentiate effect on cardiovascular system. Use with extreme caution. (7.4)
- Beta-blockers may decrease effectiveness. Use with caution and only when medically necessary. (7.5)
 Anticholinergics: May interact additively with concomitantly used
- Anticholinergics: May interact additively with concomitantly used anticholinergic medications. Avoid administration of STIOLTO RESPIMAT with other anticholinergic-containing drugs. (7.6)

-USE IN SPECIFIC POPULATIONS-

Patients with moderate to severe renal impairment should be monitored closely for potential anticholinergic side effects. (2, 8.7)

See 17 for PATIENT COUNSELING INFORMATION, Medication Guide, and Instructions for Use.

Revised: 6/2016

Instructions for Use

Tiotropium bromide and olodaterol inhalation spray

In the US: **STIOLTO**[®] **RESPIMAT**[®] (sti-OL-to-RES peh mat) (default name used below)

In the UK: **SPIOLTO**[®] **RESPIMAT**[®] (spi-OL-to-RES peh mat)

For Oral Inhalation Only

Do not spray STIOLTO RESPIMAT into your eyes.

Read these Instructions for Use before you start using STIOLTO RESPIMAT and each time you get a refill. There may be new information. This leaflet does not take the place of talking to your doctor about your medical condition or your treatment.

You will need to use this inhaler ONCE A DAY, at the same time each day. Each time you use it take TWO PUFFS.

Do not turn the clear base before inserting the cartridge.

How to store your STIOLTO RESPIMAT inhaler

- Store STIOLTO RESPIMAT at room temperature 68°F to 77°F (20°C to 25°C).
- Do not freeze your STIOLTO RESPIMAT cartridge and inhaler.
- If STIOLTO RESPIMAT has not been used for more than 3 days, release 1 puff towards the ground.
- If STIOLTO RESPIMAT has not been used for more than 21 days, repeat steps 4 to 6 under the "Prepare for first use" until a mist is visible. Then repeat steps 4 to 6 three more times.
- Keep your STIOLTO RESPIMAT cartridge and inhaler out of the reach of children.

How to care for your STIOLTO RESPIMAT inhaler

• Clean the mouthpiece, including the metal part inside the mouthpiece, with a damp cloth or tissue only, at least once a week. Any minor discoloration in the mouthpiece does not affect your STIOLTO RESPIMAT inhaler.

When to get a new STIOLTO RESPIMAT inhaler

• Your inhaler contains 60 puffs (30 doses) if used as indicated (2 puffs once daily). If you have a sample, your inhaler contains 28 puffs (14 doses) if used as indicated (2 puffs once daily).

[figure not shown]
- The dose indicator shows approximately how much medicine is left.
- When the dose indicator enters the red area of the scale you need to get a refill; there is approximately medicine for 7 days left (if you have a sample, there is approximately medicine for 3 days left).
- When the dose indicator reaches the end of the red scale, your STIOLTO RESPIMAT is empty and automatically locks. At this point, the clear base cannot be turned any further.
- Three months after insertion of cartridge, throw away the STIOLTO RESPIMAT even if it has not been used, or when the inhaler is locked, or when it expires, whichever comes first.

Prepare for first use

1. Remove clear base Safety catch Discard Keep the cap closed. by date Clear base Press the safety catch while firmly pulling off the clear base with your other hand. Be careful not to touch the piercing element. Write the discard by date on the label (3 months from the date the cartridge is inserted). 2. Insert cartridge Insert the narrow end of the cartridge into the inhaler. Narrow Place the inhaler on a firm surface and end "Click" push down firmly until it clicks into place. 3. Replace clear base Clear base Put the clear base back into place until it clicks. Do not remove the clear base or the cartridge after it has been put together. 4. Turn Arrows Keep the cap closed. Turn the clear base in the direction of the arrows on the label until it clicks (half a turn). 5. Open Cap Open the cap until it snaps fully open.

6. Press

[figure not shown]
- Point the inhaler toward the ground.
- Press the dose-release button.
- Close the cap.
- If you do not see a mist, repeat steps 4 to 6 until a mist is seen.
- After a mist is seen, repeat steps
 4 to 6 three more times.
- After complete preparation of your inhaler, it will be ready to deliver the number of puffs on the label.

Daily use (TOP)

Iurn

- · Keep the cap closed.
- Turn the clear base in the direction of the arrows on the label until it clicks (half a turn).

Open

• Open the cap until it snaps fully open.

Press

- ☐ Breathe out slowly and fully.
- Close your lips around the mouthpiece without covering the air vents.
- Point the inhaler to the back of your throat.
- While taking a slow, deep breath through your mouth, **Press** the dose-release button and continue to breathe in.
- Hold your breath for 10 seconds or for as long as comfortable.
- Repeat Turn, Open, Press (TOP) for a total of 2 puffs.
- Close the cap until you use your inhaler again.

Answers to Common Questions

It is difficult to insert the cartridge deep enough:

Did you accidentally turn the clear base before inserting the cartridge? Open the cap, press the dose-release button, then insert the cartridge.

Did you insert the cartridge with the wide end first? Insert the cartridge with the narrow end first

I cannot press the dose-release button:

Did you turn the clear base? If not, turn the clear base in a continuous movement until it clicks (half a turn).

Is the dose indicator on the STIOLTO RESPIMAT pointing to zero? The STIOLTO RESPIMAT inhaler is locked after 60 puffs (30 doses). If you have a sample, the STIOLTO RESPIMAT inhaler is locked after 28 puffs (14 doses). Prepare and use your new STIOLTO RESPIMAT inhaler.

I cannot turn the clear base:

Did you turn the clear base already? If the clear base has already been turned, follow steps "Open" and "Press" under "Daily use" to get your medicine.

Is the dose indicator on the STIOLTO RESPIMAT pointing to zero? The STIOLTO RESPIMAT inhaler is locked after 60 puffs (30 doses). If you have a sample, the STIOLTO RESPIMAT inhaler is locked after 28 puffs (14 doses). Prepare and use your new STIOLTO RESPIMAT inhaler.

The dose indicator on the STIOLTO RESPIMAT reaches zero too soon:

Did you use STIOLTO RESPIMAT as indicated (2 puffs once daily)? STIOLTO RESPIMAT will deliver 60 puffs and last 30 days if used at 2 puffs once daily. If you have a sample, STIOLTO RESPIMAT will deliver 28 puffs and last 14 days if used at 2 puffs once daily.

Did you turn the clear base before you inserted the cartridge? The dose indicator counts each turn of the clear base regardless whether a cartridge has been inserted or not.

Did you spray in the air often to check whether the STIOLTO RESPIMAT is working?

Once you have prepared STIOLTO RESPIMAT, no test-spraying is required if used daily.

Did you insert the cartridge into a used STIOLTO RESPIMAT? Always insert a new cartridge into a **NEW** STIOLTO RESPIMAT.

My STIOLTO RESPIMAT sprays automatically:

Was the cap open when you turned the clear base? Close the cap, then turn the clear base.

Did you press the dose-release button when turning the clear base? Close the cap, so the dose-release button is covered, then turn the clear base.

Did you stop when turning the clear base before it clicked? Turn the clear base in a continuous movement until it clicks (half a turn).

My STIOLTO RESPIMAT doesn't spray:

Did you insert a cartridge? If not, insert a cartridge.

Did you repeat Turn, Open, Press (TOP) less than three times after inserting the cartridge? Repeat Turn, Open, Press (TOP) three times after inserting the cartridge as shown in steps 4 to 6 under "Prepare for first use".

Is the dose indicator on the STIOLTO RESPIMAT pointing to 0? You have used up all your medicine and the inhaler is locked.

For more information about STIOLTO RESPIMAT or a video demonstration on how to use STIOLTO RESPIMAT, go to www.stiolto.com. You may also call [name] or (TTY) [name] for further information about STIOLTO RESPIMAT.

This Medication Guide and Instructions for Use has been approved by the U.S. Food and Drug Administration.

Distributed by: Boehringer Ingelheim Pharmaceuticals, Inc., Ridgefield, CT 06877 USA

 ${\sf SPIRIVA}^{\$}, \, {\sf HANDIHALER}^{\$}, \, {\sf STIOLTO}^{\$} \, \, {\sf and} \, \, {\sf RESPIMAT}^{\$} \, \, {\sf are} \, \, {\sf registered} \, \, {\sf trademarks} \, \, {\sf and} \, \, {\sf are} \, \, {\sf used} \, \, {\sf under} \, \, {\sf license} \, \, {\sf from} \, \, {\sf Boehringer} \, \, {\sf International} \, \, {\sf GmbH}.$

Copyright © 2016 Boehringer Ingelheim International GmbH ALL RIGHTS RESERVED. Revised: June 2016

Verona Pharma plc CONFIDENTIAL Page 65 of 66

